## 14.5 Reporting AEs and SAEs

The investigator will immediately report to the coordinating site PI any SAE, whether or not considered study intervention-related, including those listed in the protocol and must include an assessment of whether there is a reasonable possibility that the study intervention caused the event. Study endpoints that are SAEs (e.g., all-cause mortality) must be reported in accordance with the protocol unless there is evidence suggesting a causal relationship between the study intervention and the event (e.g., death from anaphylaxis). In that case, the investigator must immediately report the event to the sponsor.

All SAEs will be followed until satisfactory resolution or until the site investigator deems the event to be chronic or the subject is stable.

## 14.6 Unanticipated Problems

An unanticipated problem (UP), as defined by the DHHS Office for Human Research Protection (OHRP), is any incident, experience, or outcome that meets all of the following criteria:

- The incidence, experience, or outcome is unexpected given the research procedures described in protocol-related documents (e.g., the study protocol, the informed consent documents, the Investigator's Drug Brochure) and the characteristics of the subject population being studied. An event may be considered unexpected if it exceeds the nature, severity, or frequency described in the study-related documents, Investigator's Device Brochure, product labeling, or package insert.
- The incidence, experience, or outcome is related or probably related to participation in the research study. "Probably related" means the incidence, experience, or outcome is more likely than not to be caused by the research study procedures.
- The occurrence of the incidence, experience, or outcome suggests that the research places subjects or others at a greater risk of harm (physical, psychological, economic, or social) than was previously known or recognized.

The investigator will report UPs to the reviewing IRB. The UP report will include the following information:

- Protocol identifying information: protocol title and number, PI's name, and the IRB project number;
- A detailed description of the event, incident, experience, or outcome;
- An explanation of the basis for determining that the event, incident, experience, or outcome represents an UP;
- A description of any changes to the protocol, informed consent documents, or other corrective actions that have been taken or are proposed in response to the UP.

Report UPs within the timeframe(s) specified by the IRB(s) of record.

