### Relationship to Study, Study Procedure(s) and/or Study Intervention(s)

For all collected AEs, the clinician who examines and evaluates the subject will determine the AE's causality based on temporal relationship and his/her clinical judgment. The degree of certainty about causality will be graded using the categories below.

Definitely Related	Clearly related to the study procedures/intervention and other possible contributing factors can be ruled out.
Probably Related	Likely related to the study procedures/intervention and the influence of other factors is unlikely.
Possibly Related	Possibly related to the study procedures/intervention and there are other factors that could be equally likely.
Unlikely to be related	Doubtfully related to the study procedures/intervention and there is another likely cause.
Unrelated	Clearly not related to the study procedures/intervention and/or evidence exists that the event is definitely related to another cause.

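### Section 14.6 admits only events more likely than not caused by the research, so unexpected events graded Possibly Related cannot reach the IRB as unanticipated problems

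*Combined protocol and SAP*

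**What the plan says.** Section 14.6 defines an unanticipated problem conjunctively: it "is any incident, experience, or outcome that meets all of the following criteria". The three criteria are that the event is unexpected, that it is related to the research, and that it points to more risk than was previously recognised. The second reads: "The incidence, experience, or outcome is related or probably related to participation in the research study". Section 14.6 adds that probably related "means the incidence, experience, or outcome is more likely than not to be caused by the research study procedures". Unanticipated problems are reported to the reviewing IRB.

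The scale that staff use to grade causality is in 14.3, under Relationship to Study. It has five grades. Probably Related is defined as "Likely related to the study procedures/intervention and the influence of other factors is unlikely". Possibly Related is defined as "Possibly related to the study procedures/intervention and there are other factors that could be equally likely". The grading is done at the bedside: "the clinician who examines and evaluates the subject will determine the AE's causality based on temporal relationship", together with clinical judgment.

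Two neighbouring sections matter. Section 14.5 has every SAE reported to the coordinating site PI, whatever its judged cause, and the report "must include an assessment of whether there is a reasonable possibility that the study intervention caused the event". Section 14.7 requires a report to the IRB within 5 working days for serious unanticipated effects caused by a device or associated with one, and for other serious unanticipated problems associated with a device.

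**The concern.** The grade that staff assign under 14.3 decides in practice whether an event counts under 14.6, and 14.6 has no place for Possibly Related. An event can be unexpected, can suggest that subjects face more risk than was known, and still not be an unanticipated problem because another cause cannot be ruled out.

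This matters more in a first study in a new population. The team's own experience with the multi-network schedule, described in 5.4, is five healthy adults. Subjects here have amnestic MCI, and 5.1 gives 10 to 15% yearly progression from MCI to AD. A non-serious, unexpected cognitive worsening would therefore have a ready alternative explanation, and cognitive worsening is not among the interventional risks listed in 13.2. The documents do not say how such an event would be graded. If it were graded Possibly Related, 14.6 would exclude it.

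**Working it through.** The plan states no figure on this point, so the check sets the sections side by side.

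**1. Does Possibly Related fail 14.6?** Let p be the judged probability that the research caused the event and q the probability of other causes, with p + q = 1. Section 14.6 requires p > 0.5. The 14.3 grade leaves open that q equals p, and then p = 0.5, which is not above 0.5. An assessor who holds that other causes may be equally likely cannot also assert that the research is the more likely cause. Because all three criteria must hold, failing this one is decisive. The bare word related in 14.6 does not help: it is the stronger partner of probably related, so it cannot sit below the 0.5 line.

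**2. Do 14.3 and 14.6 mean the same by probably related?** No. Take an event judged 60% likely to be due to the research (an illustrative figure). It meets 14.6, since 0.60 > 0.5. Under 14.3, other causes carry 1 - 0.60 = 0.40, which is hard to call unlikely, so the event may not earn the Probably Related grade. Whether it is reported then depends on whether staff go by the grade or by the sentence in 14.6. No mapping is given.

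**3. Is there another event-level route to the IRB?**

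| Section | What it covers | Reaches the IRB? |
|---|---|---|
| 14.5 | All SAEs, to the coordinating PI; in one stated case to the sponsor | No IRB report named |
| 14.6 | Unexpected, more likely than not caused, greater risk | Yes |
| 14.7 | Serious, unanticipated, caused by or associated with a device | Yes, within 5 working days |
| 14.9 | Two-monthly review by investigators and core staff | No IRB report named |
| 16.1 | Passes on reportable events, with unanticipated problems as an example | Relies on the 14.6 definition for those |

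**4. What is left over?** Section 14.7 speaks of a device in general. Sections 10.1 and 13.2 describe the MRI scanner as an investigational device, and 10.1 says the same of the head coil, so serious unanticipated MRI-associated problems go through 14.7. Nothing there excludes TMS equipment. Training is delivered during stimulation (9.1), so many serious events in a session could also be called device-associated. The remainder is non-serious events, and serious events with no device association, graded Possibly Related.

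**The case against.** The best case against the point is that the harms of most concern in a stimulation pilot are serious and device-associated, and 14.7 handles those with a lower causal bar and a short deadline. In addition, 14.4 records all AEs whatever their cause, 14.9 reviews safety every two months, 14.10 has the IRB told of any suspension or termination, and 16.1 feeds site information into continuing review. Section 14.6 also presents its definition as OHRP's, so reporting beyond it is a policy choice. All of this stands and narrows the consequence. None of it gives an event-level IRB report for the remaining events. Whether 14.6 matches the OHRP wording cannot be checked from these documents.

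Three stronger readings are tempting and are not supported.

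- A reader might infer that a blinded assessor could rarely reach the 14.6 standard. Section 9.1 describes blinding of the subject and device operator; the blinding of the clinician who grades causality is not stated, and 9.3 allows emergency unblinding. Section 14.6 asks about research procedures generally, so for harms from cap, gel, training, testing or MRI the arm is irrelevant. A calculation from an assumed rate ratio between arms would ignore timing, which 14.3 makes part of the judgment.
- A reader might infer that serious MRI or TMS events have no path to the IRB. Section 14.7 provides one when they are unanticipated and associated with the device.
- A reader might see 14.5 as setting a competing, lower reporting threshold. It does not: SAEs are reported regardless of cause, and reasonable possibility is something the report must assess, not a condition for making it.

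**Conclusion.** The point holds in a limited form. By its own words 14.6 excludes events that meet the 14.3 definition of Possibly Related, and the two sections disagree on what probably related means. The gap covers non-serious events, and serious events not associated with a device, that are unexpected, suggest greater risk and carry that grade. How many there would be among 20 subjects cannot be estimated from the documents. The conclusion rests on reading the 14.3 grades as the input to 14.6, which the shared terms suggest but the protocol does not state. It concerns safety oversight only; the completion-rate analysis is unaffected. It is still worth correcting, because this is a written rule that keeps some unexpected harms from the IRB, in a trial whose own prior multi-network experience is five healthy adults.

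**What to change.** In 14.6, extend the relatedness criterion to events with a reasonable possibility of having been caused by the research procedures. State that the 14.3 grades Possibly, Probably and Definitely Related all satisfy it. This also settles the two meanings of probably related, since the boundary between Possibly and Probably would no longer decide reporting. Leave the unexpectedness and greater-risk criteria as they are; they keep the added reporting in bounds.

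Before changing the text, check it against the OHRP source that 14.6 names and against the reviewing IRB's policy. If the definition should stay as attributed, keep it and add a sentence making the wider reporting a protocol requirement on top of it.

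The cost is about one sentence of protocol text, submitted as an amendment, and a few more IRB reports in a 20-subject trial.

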## 14.7 Unanticipated Adverse Device Effect

An unanticipated adverse device effect means any serious adverse effect on health or safety or any life-threatening problem or death caused by, or associated with, a device, if that effect, problem, or death was not previously identified in nature, severity, or degree of incidence in the investigational plan or application (including a supplementary plan or application), or any other unanticipated serious problem associated with a device that relates to the rights, safety, or welfare of subjects (21 CFR 812.3(s)).

An investigator shall submit to the reviewing Institutional Review Board (IRB) a report of any unanticipated adverse device effect occurring during an investigation as soon as possible, but in no event later than 5 working days after the investigator first learns of the effect.

## 14.8 Incidental Findings

### MR image clinical abnormality

If there are any clinically relevant adventitious findings from the baseline or follow-up visits, subjects will be informed; however subjects may not be informed of findings of questionable significance. Participants will be contacted directly (either on the phone or in person) if the results of an imaging study are clinically significant. The clinician will confer with the subject about whether they would like their primary care provider to be notified about any clinically significant findings and contact them if desired.

## 14.9 Study Monitoring

The Principal Investigators (PIs) will be responsible for ensuring participants' safety on a daily basis.

In addition, the PI, Co-Is and core research staff will meet every two months to monitor study progress and any data and safety issues will be reviewed.

All unanticipated problems and complications will be discussed during regular staff meetings (attended by PI, supervisors, and coordinators) during which a plan of action will be formulated and implemented.

## 14.10 Study Stopping Rules

This study may be temporarily suspended or prematurely terminated if there is sufficient reasonable cause. Written notification, documenting the reason for study suspension or termination, will be provided by the suspending or terminating party to the investigators. If the study is prematurely terminated or suspended, the PI will promptly inform the IRB and will provide the reason(s) for the termination or suspension.

Circumstances that may warrant termination or suspension include, but are not limited to:

- Determination of unexpected, significant, or unacceptable risk to subjects
- Insufficient compliance to protocol requirements
- Data that are not sufficiently complete and/or evaluable

Study may resume once concerns about safety, protocol compliance, data quality are addressed and satisfy the applicable federal and institutional regulatory authorities.

## 15.0 STUDY FEASIBILITY

### 15.1 Economic Burden to Subjects

Subjects will not have to pay for study procedures.

### 15.2 Feasibility of Recruiting the Required Number of Subjects

**Recruitment sources:** Participants may be recruited by several methods. Major sources are summarized below:

- 1) Physician Referrals (e.g. from a Memory Assessment Clinic [University of Wisconsin (UW) Hospital and Clinics' Memory Clinics and the Memory Disorder's Clinic in Neurology at Froedtert and the Medical College of WI, Middleton VA Hospital Madison, Froedtert Hospital, MCW Memory Disorders Clinics and the Geriatric Psychiatry Clinic]; the Wisconsin Alzheimer's Institute (WAI) Diagnostic Clinic Network).
- 2) Participants from the community (through advertisements, brochures, educational /outreach events, etc.)
- 3) From existing large studies such as the Wisconsin Alzheimer's Disease Research Center clinical core. In addition, we will approach participants who have provided permission to be contacted for future research as part of their participation in Wisconsin ADRC-affiliated studies.

4) WI ADRC Recruitment Registry (REGGIE, 2011-0772) and the Alzheimer's Association Trial Match website.

To maximize retention, study personnel may travel to participants' homes to perform interventions.

## 16.0 MULTISITE RESEARCH CONSIDERATIONS

### 16.1 Single IRB (sIRB) Communication Plan

#### ***Study Team Communication Plan***

Study initiation conference calls will include a presentation by the reliance site's PI to inform all sites about the reliance arrangement as well as the review processes and reporting requirements of the Reviewing IRB

[name] or his delegate will be responsible for ensuring ongoing communication with all participating study teams via teleconferences and regular emails throughout the study. Key communication points will occur to:

- Disseminate IRB determinations and IRB-approved documents
- Educate study teams regarding the approved study and amendments to the study
- Alert study teams to problems that may affect the conduct of the study or the rights and welfare of research participants, such as unanticipated problems and serious noncompliance
- Inform study teams of any changes in study status (e.g., temporary suspensions of recruitment) or new information
- Facilitate submissions to the Reviewing IRB, including:
  - Inclusion of site-specific requirements in consent documents
  - Identification of any variability in study implementation across sites that must be communicated to the Reviewing IRB
  - Collection of information from participating sites to include in continuing review reports to the Reviewing IRB
  - Site-specific amendments
  - Personnel updates (as required by the Reviewing IRB)
  - Reportable events (e.g., noncompliance, unanticipated problems)
  - Closure reports
- Ensure revisions to applicable conflict of interest management plans are provided to the Reviewing IRB

